3.4. EPAD LCS Data Sources and Collection

The only data source for this study will be the data collected as part of the EPAD LCS study. Electronic data capture will be used as appropriate, e.g. for cognitive and imaging data. Central laboratories will be used for all CSF and genetic assessments, and central reading of all neuroimaging will be undertaken. CDR raters, where possible, should be blinded to all other cognitive and clinical assessments, except if biomarker status is disclosed. Overall probability for developing AD dementia will not be disclosed to research participants due to insufficient accuracy of current disease models, but will be disclosed at participant's request. However, findings with established clinical relevance will be disclosed to participants and, with their consent, to their treating physician for initiation of appropriate treatment.

The assessments chosen for EPAD LCS are based on recommendations developed by five Scientific Advisory Groups (SAGs) within EPAD (Clinical and Cognitive Outcomes, Epidemiology, Fluid Biomarkers, Genetics, and Imaging). The SAGs each have approximately six expert members, as well as external advisors. SAGs recommendations were based on reviewing the current literature, following widely accepted practices, and minimizing participant burden.

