
² Continued participation in the Parent Cohort is expected.

	
considered an exclusion criterion. Co-enrolment in the Amyloid Imaging to Prevent Alzheimer’s Disease (AMYPAD) Prognostic and Natural History Study (PNHS) is not considered to fall under this exclusion criteria.
 
 • Diminished decision-making capacity/not capable of consenting at screening visit • Unable to comply with protocol requirements in the opinion of the investigator
DATA SOURCES AND COLLECTION	
The only data source for this study will be data collected as part of EPAD LCS. Electronic data capture will be used, e.g. for cognitive and neuroimaging data. A central laboratory will be used for all genetic and biomarker measurements, and central reading of all neuroimaging will be undertaken. CDR raters, where possible, should be blinded-to all other cognitive and clinical assessments, except if biomarker status is disclosed. Overall probability for developing AD dementia will not be disclosed to research participants due to insufficient accuracy of current disease models. However, findings with established clinical relevance will be disclosed to participants and, with their consent, to their treating physician for initiation of appropriate treatment.

PRIMARY OUTCOMES	
Cognitive outcomes – RBANS Total Scale Index Score³
 
 - Verbal Episodic Memory: List Learning & Story Memory (RBANS) - Visual Episodic Memory: Figure recall (RBANS) - Visuospatial/Constructional: Figure Copy & Line Orientation (RBANS) - Language: Picture Naming (RBANS) - Attention/Executive Functioning: Semantic Fluency, Digit Span, Coding (RBANS)
SECONDARY OUTCOMES	
Cognitive Outcomes
 
 - Working Memory: Dot Counting (NIH EXAMINER) - Choice Reaction Time and Set Shifting: Flanker (NIH EXAMINER) - Paired Associate Learning: Favourites (University of California, San Francisco) 
CSF biomarker outcomes
 
 - Aβ, t-tau, p-tau 
Neuroimaging outcomes (MRI)
 
 - Hippocampal & whole brain volume

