 - *Clinical Dementia Rating Scale (CDR)*. The CDR³² is comprised of two separate semi-structured face to face interviews one with the individual and another with a reliable collateral source (informant, i.e., partner, family member or relative, friend, or any other closely related individual) conducted by blinded independent, CDR certified Raters. Raters that conduct the CDR assessment on a particular research participant cannot rate any other assessments for that participant. During the interview, the clinician assesses the participant's current status in six domains (memory, orientation, judgment and problem solving, community affairs, home and hobbies, and personal care) and rated accordingly using a 5-point scale (0 = no impairment, 0.5 = questionable impairment, 1=mild dementia, 2 = moderate dementia, 3 = severe dementia, <http://knightadrc.wustl.edu/cdr/aboutcdr.htm>). Outcome measures of the CDR are a Global CDR score (derived from an algorithm developed by the The Charles F. and Joanne Knight Alzheimer's Disease Research Center [Knight ADRC]), the CDR sum of boxes (CDR-sb, the sum of all six domains), and a CDR rating for each domain. CDR raters, where possible, should be blinded, as far as possible, to all other cognitive and clinical assessments, except if biomarker status is disclosed. The rationale for the CDR rater remaining blinded is that if they know the status of the biomarker tests, or result of any other tests this could potentially influence how they score participants undertaking a CDR test.

-
- *Physical examination*, including e.g. neurological examination, blood pressure and pulse measurements.

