6.3. Potential Disclosure of Risk Information

Given that one of the objectives of EPAD LCS is disease modelling, EPAD LCS will have a probability-spectrum population covering the entire continuum of probability for AD dementia development. As accurate disease models covering the entire course of AD before dementia development are currently lacking, EPAD LCS will apply a policy of non-disclosure of overall probability. Disclosure will take place in case this is specifically requested by a participant i.e. results can be made available to a participant on their request. CDR raters, where possible, should be blinded to all other cognitive and clinical assessments, even if biomarker status is disclosed.

Investigators cannot be blinded to results of some cognitive tests and related clinical assessments. Such results may be disclosed to research participants because these assessments are routinely used in clinical practice, and a dementia diagnosis or CDR ≥ 1 represent exclusion criteria at baseline. EPAD LCS participants will be individuals with no or only minor impairments, but some of them may develop dementia during the course of the study. In the event that a research participant has CDR ≥ 1 , or the investigator observes significant cognitive and functional decline suggestive of dementia development, the research participant will be referred to their primary care physician for appropriate monitoring and treatment.

The EPAD LCS information and consent process will carefully explain the uncertainties associated with biomarker testing, including the lack of clinical validation and the absence of a definite pathway between probability and disease state. EPAD LCS research participants will also be informed that, for some of them, a later invitation to participate in the EPAD PoC trial may mean learning about some of the components/dimensions in their probability status at the time of trial participation. Written and visual education materials will be provided to participants at LCS study recruitment to enable them to make an informed decision about whether they want to learn this information. Ongoing communication with research participants (described in Section 6.6 Ongoing Communication with Research Participants) will be used to address any stressful situations that may occur during recruitment and course of the study.

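### The protocol gives opposite rules on whether CDR raters stay blinded once biomarker status is disclosed, and the more frequent wording conflicts with its own rationale

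*Protocol*

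**What the plan says.** Four places in the current protocol state the rule for CDR rater blinding.

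- Synopsis, Data Sources and Collection: "CDR raters, where possible, should be blinded-to all other cognitive and clinical assessments, except if biomarker status is disclosed".
- Section 3.4: "CDR raters, where possible, should be blinded to all other cognitive and clinical assessments, except if biomarker status is disclosed".
- Section 3.4.6, CDR entry: "CDR raters, where possible, should be blinded, as far as possible, to all other cognitive and clinical assessments, except if biomarker status is disclosed".
- Section 6.3: "CDR raters, where possible, should be blinded to all other cognitive and clinical assessments, even if biomarker status is disclosed".

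The CDR entry in section 3.4.6 also describes the interviews as "conducted by blinded independent, CDR certified Raters" and bars the CDR rater from rating anything else for the same participant. It gives the reason for blinding: "if they know the status of the biomarker tests, or result of any other tests this could potentially influence how they score participants".

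Disclosure is foreseen. Section 6.3 states that "results can be made available to a participant on their request".

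**The concern.** In three places the requirement to blind the rater lapses once biomarker status is disclosed. In the fourth it continues. A site cannot follow both rules, and nobody can say which conduct would be a deviation under section 7.2.

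The exception also works against its purpose. Section 3.4.6 blinds the rater because knowledge of biomarker or other results could shift the score, yet the same entry waives the blind in a situation where such knowledge becomes more likely. Read literally, the waiver reaches further still: disclosure of biomarker status releases the rater from blinding to all other cognitive and clinical results.

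What is at stake is the CDR as a staging measure. A rating of 1 or more excludes at screening, and the CDR is scheduled at Visit 1 and at every follow-up visit. If known biomarker status influences some ratings, and disclosure is itself related to that status, the resulting error in the CDR is not random with respect to the biomarkers.

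**Working it through.** The core of this point is a comparison of text. The protocol has no figure to reproduce.

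**Step 1: the rules side by side.** All four sentences share the same subject (CDR raters), the same qualifier (where possible) and the same object (other cognitive and clinical assessments). They differ in the last clause. Three make disclosure an exception (synopsis, 3.4, 3.4.6) and one makes it irrelevant (6.3). The count is 3 against 1. All four are current text, and the log of changes for Version 5.0 attributes both wordings to that same amendment, so neither can be set aside as older text.

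**Step 2: the rules against the rationale.** Section 3.4.6 gives knowledge of biomarker tests, or of any other test, as a possible influence on scoring. Keeping the blind after disclosure follows from that reason. Lifting it does not. Only the section 6.3 wording is consistent with the rationale.

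**Step 3: scope.** None of the four sentences names CSF, MRI or APOE results as something the rater should not see, although the rationale expressly covers biomarker tests.

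**Step 4: who could be affected.**
- Participants who ask for their results (3.4, 6.3).
- Participants who enter with an amyloid PET result from the previous 12 months that both they and the trial delivery centre know (3.4.3). Here the knowledge can precede the Visit 1 CDR.
- Participants told why they may be eligible for the PoC trial (6.2 c) who later return to the LCS (3.5). The transition visit is otherwise the last LCS visit, and the data collection schedule has no CDR there.

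**Step 5: size.** No disclosure rate is given, so any figure is an illustration. Assume no true association, 20% rated CDR 0.5 in both biomarker groups, and a shift that occurs only where status is known.

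Status known for everyone:
- +5 points in positives: (0.25/0.75)/(0.20/0.80) = 1.33
- +10 points in positives: (0.30/0.70)/(0.20/0.80) = 1.71
- +5 in positives and −5 in negatives: (0.25/0.75)/(0.15/0.85) = 1.89

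Status known for 20% (assumed), so that each shift is multiplied by 0.2:
- +1 point: (0.21/0.79)/(0.20/0.80) = 1.06
- +2 points: (0.22/0.78)/(0.20/0.80) = 1.13
- +1 and −1 point: (0.21/0.79)/(0.19/0.81) = 1.13

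The base rate, the shifts and the fraction known are all assumptions. The result depends heavily on the disclosure rate, which the documents do not supply.

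**The case against.** The best defence is that the exception only acknowledges reality: a participant who knows the result may mention it in the interview, so blinding cannot be promised. That is fair, but the qualifier where possible stands in all four sentences and already covers unavoidable unblinding. The exception adds only permission to stop trying.

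Several stronger readings are tempting and are not supported.

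- **That raters are unblinded after disclosure.** The exception waives a soft requirement. No sentence orders that raters be told anything, and section 3.4.6 still calls for blinded, independent raters.
- **That biomarker knowledge is named as the main threat.** Section 3.4.6 mentions it together with any other test and does not rank them. That sentence also shows that the intended blind already reaches biomarkers, so the scope gap in Step 3 is one of wording.
- **That the CDR is modelled against the biomarkers, so their association is partly manufactured.** The protocol states no CDR model. The CDR is an other measure, described in section 3.4.6 as principally a clinical descriptor. Composite-level modelling uses the RBANS Total Scale Index (4.3), and physician-diagnosed dementia is collected separately. The CDR could enter through the clinical profiles mentioned in section 4.2, but that is an inference.
- **That every PoC invitee contributes biased ratings.** Only those who return to the LCS have later CDRs.
- **That baseline eligibility is widely exposed.** CSF is normally taken at Visit 1 and measured centrally, so prior knowledge is largely confined to people with an earlier result.
- **That biased ratings decide who stops MRI and CSF sampling.** That rule needs a CDR above 1, which on the global scale means at least 2. An illustration at CDR 0.5 says nothing about that threshold.

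**Conclusion.** The contradiction is certain, because it is visible in four current sentences, and the exception conflicts with the protocol's own reason for blinding. It should be corrected.

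The consequence is limited. It concerns CDR ratings in participants whose biomarker status is disclosed while they are in the LCS. A reader might infer that the main result is threatened, but the primary endpoint is the RBANS Total Scale Index Score, which the CDR blinding rule does not directly touch. That the ratings could be influenced rests on the protocol's own statement. How often or how strongly cannot be determined from the documents, and the odds ratios above are not estimates for this cohort. The point therefore merits a should-fix rating. A must-fix rating is not supported.

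**What to change.** Use one sentence in the synopsis and in sections 3.4, 3.4.6 and 6.3. The section 6.3 version, which keeps the blind even if biomarker status is disclosed, is the one consistent with the rationale in section 3.4.6. In the same sentence, name biomarker, MRI and genetic results among what the rater should not see where possible.

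The cost is a wording change in four places. No additional rater is needed, because section 3.4.6 already requires a CDR rater who rates nothing else for that participant.

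An optional addition is one eCRF item at each CDR recording whether the rater knew the biomarker status. It adds a little site administration and would allow a later sensitivity analysis without those ratings. Resolving the contradiction does not depend on it.

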3.4.1. Cognitive Outcomes

Both research and clinical trials in AD have been highly heterogeneous in their choice of clinical and cognitive outcomes and even more diverse in the type of measures used to capture and quantify them. This heterogeneity has reflected not only the constant evolution of scientific knowledge about brain functioning and its functional correlates but also commercial interests, personal preferences, subject tolerance and concerns over acceptability to regulatory authorities. Within this context the EPAD project presents two further challenges: [1] the outcomes refer to a greater distance from clinical AD diagnosis than has been attempted in previous trials, and [2] the outcome measures should be scientifically objective and unlikely to be seen as favouring a specific EPAD PoC trial sponsor.

Given these issues, the EPAD Clinical and Cognitive outcomes SAG was tasked with formulating recommendations for the ENE based on an objective extensive review of current knowledge on the early, asymptomatic stage of AD. The following criteria were used to compare the relative merits of different tests:

- Available translations

-
- Good psychometric properties (priority was given to measures with high sensitivity rather than specificity, as the battery is for signal detection and not diagnosis)
 - Alternative forms or ability to easily create fully alternative versions, to permit retesting more than once per year (particularly important as some research participants in EPAD LCS may be recruited into the EPAD PoC trial later on)
 - Validated preferably by reference to longitudinal data in relation to either preclinical through prodromal AD^{8,9,10} populations, APOE genotype or amyloid positivity
 - Normative data available
 - Limited (or well-defined) practice effects
 - Preference for non-proprietary material (for previously existing tests)
 - Suitable for non-specialist administration

The final ENE battery was thus chosen to adequately cover all relevant cognitive domains, with greatest possible sensitivity to early-stage changes, cross-cultural transferability, and availability of parallel forms, while also providing both accuracy and processing time measures. A total battery administration time of approximately 2 hours including breaks was designed to minimize the burden for participants. Because EPAD LCS needs to provide a trial readiness cohort for the EPAD PoC trial, the EPAD cognitive test battery was also developed to be “modulable”, i.e. to allow individual components to be selected out corresponding to specific drug targets if necessary during the EPAD PoC trial. In addition, each component task will have four alternative forms for retesting.

The ENE battery will be administered using an electronic tablet device, every six months during the first year, and then annually to all participants in EPAD LCS. Results from these testing waves will provide normative data for the cohort for either the whole population or sub-groups. The ENE battery is summarized in Table 2 and described in detail below according to the order of test administration.

Table 2: Cognitive outcomes⁸

Cognitive domains	Tests
	Primary outcomes
Verbal Episodic Memory	List Learning & Story Memory (RBANS)
Visual Episodic Memory	Figure Recall (RBANS)
Visuospatial/Constructional	Figure Copy & Line Orientation (RBANS)
Language	Picture Naming (RBANS)
Attention/Executive Functioning	Semantic Fluency, Digit Span, Coding (RBANS)
	Secondary outcomes
Working memory	Dot counting
Choice reaction time and set-shifting	Flanker
Paired associate learning	Favourites (Learning, Delay & Recognition)
	Exploratory outcomes
Allocentric space	Four Mountains Task
Egocentric space	Supermarket Trolley Virtual Reality

As noted above in Table 2, for statistical purposes the RBANS Total Scale Index Score will serve as the Primary Endpoint. In addition, all Clinical Outcome Assessments (COAs) measuring cognition were categorized by validation level as denoted in Table 2 above. For LCS purposes, Primary outcomes include anchor or criterion measure(s) that have been accepted by regulatory authorities in previous registration trials. The RBANS will serve as the criterion measure for this study. Secondary outcomes are those either in need of additional psychometric validation, validation of alternative forms and/or lack normative data. As reflected in Table 2, the Dot counting, Flanker and Name/Face pair measures fall into this category. Exploratory outcomes are those untested in large population-based studies and/or in need of psychometric validation. The Four Mountains and Supermarket Trolley tests are exploratory outcomes in this LCS.

An additional goal of the LCS is to help validate the secondary and exploratory cognitive outcome measures against a known and accepted criterion measure. Specifically, through validation within the LCS the Secondary outcome measures may be potentially considered to be used as a Primary Endpoint in future proof of concept or registration trials. The exploratory outcome measures would require two independent studies with convergent findings for full psychometric validation. Thus, the LCS will help provide initial evidence for the exploratory outcomes to be potentially elevated to secondary endpoint status in future studies or trials (e.g., EPAD PoC study).

In order to meet Good Clinical Practice (GCP) requirements, computerized measures must comply with Title 21 CFR Part 11/European Union Annex 11. Although the EPAD LCS is done in compliance with GCP, including the Primary Endpoint, it should be noted that the computerized

⁸ For statistical purposes, the RBANS Total Scale Index Score will serve as the Primary Endpoint.

secondary and exploratory measures are undergoing additional validation in this LCS and, thus, do not yet fully meet GCP.

Verbal Episodic Memory

a. List Learning/Recall (RBANS)^{11,12}

List Learning measures rote verbal memory for unrelated information. In the immediate recall subtest, the participant hears a list of 10 semantically unrelated words and must repeat the words back to the examiner. The word list is presented to the participant a total of four times, evaluating ability to learn verbal information after repeated exposure. For List Recall, after a delay with intervening tasks, the participant will recall the 10 words learned in the List Learning subtest. Immediately following the participant is read 20 words (i.e., 10 targets, 10 foils) and asked to respond ‘yes’ or ‘no’ to indicate whether each word was on the word list.

b. Story Memory (RBANS)^{11,12}

The task measures memory for conceptually related verbal information. The participant hears a story that is two sentences in length and must repeat the story back to the examiner. The participant hears the story two times; therefore, the subtest also measures verbal learning. Following a delay with intervening tasks, the story is recalled to assess long-term verbal memory encoding and retrieval.

Visual Episodic Memory and Visuospatial/Constructional Analysis

a. Figure Copy (RBANS)¹¹

The Figure Copy task requires the copying of a complex geometric design from a model, implicating visuospatial reasoning, attention to visual details, motor programming, and, to a lesser degree, organization and fine-motor ability. After a delay, the figure is redrawn from memory without prior warning to measure long-term free recall for conceptually-related visuospatial information and incidental memory (i.e., memory for information that was encoded without specific effort to do so).

b. Line Orientation (RBANS)¹¹

The Line Orientation task assesses the ability to correctly identify the angle and spatial orientation of lines in two-dimensions. The participant is presented a drawing with 13 equal lines fanning out in different directions from a central point, all lines are numbered (1-13). Below this drawing is another containing only two lines from the above array, and they are asked to identify what two number lines the drawing matches.

Language

Picture Naming (RBANS)^{11,12}

The Picture Naming task measures confrontation naming skills. This is a direct assessment of expressive language skills often impaired in global and specific types of aphasia, specifically dysnomia. The participant is shown 10 drawings of common objects and asked to name each one. The drawings are simple line drawings to avoid any perceptual confusion that more complex drawings may create.

Attention/Executive Functioning

a. Semantic Fluency (RBANS)^{11,12}

The Semantic Fluency task measures the participant's ability to retrieve and express words using a semantic prompt. This is a direct assessment of expressive language skills often impaired in global and expressive aphasia. The participant is asked to say as many words as possible associated with a specific category (e.g., fruits and vegetables) of objects within a fixed time limit.

b. Digit Span (RBANS)^{11,13}

The Digit Span subtest is a measure of auditory registration and brief focused attention. The participant listens to a series of digits read out by the examiner at one per second (e.g., 2–9) and is asked to repeat the digits in the same order.

c. Coding (RBANS)³⁷

The Coding subtest is a measure of brief, focused, visual attention, visual scanning and processing speed. Participants are presented a page containing a key at the top containing symbols, and an associated number below each (1-9). The rest of the page contains rows of boxes with symbols (in a random sequence), and a blank box below each. Using the key, the participant is asked to fill in the number corresponding to each symbol, as quickly as possible and complete as many in order in 90 seconds.

Working Memory

Dot Counting (NIH EXAMINER)¹⁵⁻¹⁸

This verbal working memory task is presented on a computer screen as a mixed array of green circles, blue circles and blue squares, and the participant is instructed to count all of the blue circles on the screen and remember the final total. The examiner then switches the display to a different mixed array of green circles, blue circles and blue squares. The participant is instructed to count the blue circles in the new display. The number of different displays presented to the participant in each trial increases from two to seven over six trials. After counting the blue circles on all of the displays presented within a trial, the participant recalls the total number of blue circles in each of the different displays in the order in which they were presented.

Choice reaction time and set-shifting

*Flanker (NIH EXAMINER)*¹⁵⁻¹⁸

The Eriksen Flanker Task is a set of response inhibition tests used to assess the ability to suppress responses that are inappropriate in a particular context. The target is flanked by non-target stimuli which correspond either to the same directional response as the target (*congruent* flankers), to the opposite response (*incongruent* flankers), or to neither (*neutral* flankers). In the tests, a directional response (usually left or right) is assigned to a central target stimulus. Various forms of the task are used to measure information processing and selective attention.

Paired-Associate Learning

Favourites (Immediate Recall, Delayed Recall, and Recognition) (University of California, San Francisco)^{19,20}

On the Favourites Memory task, participants are asked to remember people and their favourite food and animal. On both learning trials, participants are shown each of four different faces twice, each paired once with a favourite vegetable / fruit name and once with a favourite animal name. Each pair is shown for 5 seconds in a pseudorandom order. After each learning trial, the faces reappear one at a time, and the participant is asked to recall the food and the animal associated with that face. After 10 minutes, delayed recall and recognition trials are administered.

Allocentric Space

Four Mountains Task (University College London/University of York)^{21,38}

The test assesses linkage between the episodic and spatial functions of the hippocampus, which permits representation of spatial information in an allocentric form and hence encoding of the context in which events occur. Computer-generated landscapes comprised of four hills (of varying shape and size) surrounded by a distant semi-circular mountain range are presented with a sample image for 10 seconds following which the participant is immediately presented with four alternative images, one of which (the target image) shows the same topography as the sample image, seen from a novel viewpoint, from which they must identify the target image by pressing a key. Non-spatial features (lighting, vegetation, weather conditions) of both target and foil landscapes are varied between presentation and testing, such that transient local features of the image cannot be relied on to solve the task.

Navigation in Egocentric Space

*Virtual Reality Supermarket Trolley (University College London)*²²

This test, which is sensitive to deterioration in the precuneus, retrosplenial cortex and entorhinal connections measures egocentric spatial orientation (as opposed to allocentric space) through presentation of 14 video vignettes in an ecological virtual supermarket from a first person

perspective. A route through the supermarket in which the participant is behind the trolley involves a series of 90° turns, and at the end the participant is required to point in the direction of the entry.

